**Antenatal ThREe Steps Perineal mASSage in reducing perineal trauma and post-partum morbidities: TRESPASS clinical study**

**PROTOCOL SYNOPSIS**

Title	Antenatal ThREe Steps Perineal mASSage in reducing perineal trauma and post-partum morbidities: TRESPASS clinical study
Sponsor	Azienda Sanitaria Universitaria Friuli Centrale (ASUFC)
Principal investigator	Dott.ssa [name]
Study collaborators	Dott. [name], Dott.ssa [name], Dott.ssa [name], Dott. [name], Dr.ssa [name], Dott. [name], Dr.ssa [name], Prof. [name],
Rationale	Perineal trauma from delivery correlates with an increased incidence of perineal pain and discomfort, dyspareunia and sexual dysfunction, as well as urinary and anal incontinence and therefore have a significant impact on women's physical and mental health. Prepartum perineal massage has been shown to reduce the incidence of spontaneous vagino-perineal tears and promote better anatomo-functional recovery of the perineum in the postpartum period. To date, there are no guidelines on the best modes of perineal massage, and there is a lack of true standardization of the process in the literature. Investigating the relationship between prepartum perineal massage and perineal tears (and related short- and long-term morbidity) could lead to improvement in obstetric clinical practice by giving the right guidance to the pregnant woman in pelvic floor education.
Endpoint	The authors developed, on the basis of the evidence available at the present time, a peculiar type of perineal massage, embedded in a standardized clinical process including training and follow-up of the patient. Thus, the primary endpoint of the present study is to assess the difference in incidence in the two study groups of the absence of vagino-perineal tears (intact perineum). Secondary endpoints to be assessed are the superiority of perineal massage on the duration of the second stage of labor, on incidence of operative delivery and episiotomies, and on perineal pain and dyspareunia in postpartum.
Type	Prospective randomized superiority trial.
Participating centers	ASUFC - Clinic of Obstetrics-Gynecology, Santa Maria della Misericordia Hospital of Udine
Study duration	2 years
Period of observation	2024-2026
Sample size	154 patients (77 for each arm).
Statistical analysis	Quantitative variables will be described with mean and standard deviation; qualitative variables will be summarized in percentages and frequency indices. Continuous and categorical data will be compared with Student's t test and Fisher's exact test, respectively. Relationships between the data will be expressed using Relative Risk with confidence intervals. A p-value < 0.05 will be considered statistically significant.
Population and data sources	Pregnant women referred to the Udine Obstetrics Clinic who meet the inclusion criteria. Data are collected from the patient history and clinical interview, medical records and partograms, data collection form and written questionnaires; they will be entered into a computerized database in which the patient's name will be replaced by a progressively increasing number to preserve anonymity.
Inclusion criteria	
 
- Single pregnancy
 
- Part presented cephalic
 
- Age between 18 and 40 years
 
- Pregravid body mass index (BMI) between 18 and 29.9
 
- Understanding of the Italian language
 
- Estimated Fetal Weight in range (3rdcentile to 97thcentile according to Intergrowth)
 

Study design	All pregnant patients who meet the inclusion criteria will be selected and offered participation in the study by delivering the information brochure at the 2nd trimester obstetrical visit. If at the 3rd trimester obstetrical visit the patient expresses willingness to participate in the study, consent will be signed and enrollment and randomization to the study will be performed. The patient will then be notified of the date of the training meeting

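### Second-stage duration is tested without adjusting for parity: valid, but a parity covariate estimates the same mean difference and gains power if durations differ by parity

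*Protocol*

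**What the plan says.** The Endpoint row of the protocol synopsis lists, among the secondary endpoints, "the superiority of perineal massage on the duration of the second stage of labor". The Type row describes a "Prospective randomized superiority trial", and the Sample size row gives 154 women, 77 per arm.

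The Statistical analysis row sets the method for all outcomes: "Continuous and categorical data will be compared with Student's t test and Fisher's exact test, respectively". It adds "A p-value < 0.05 will be considered statistically significant". No covariate and no stratification factor is named.

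The Inclusion criteria row has six items: singleton pregnancy, cephalic presentation, age, pregravid BMI, understanding of Italian and estimated fetal weight. None concerns parity, and parity is mentioned nowhere in the document. On sources, the synopsis states "Data are collected from the patient history and clinical interview, medical records and partograms".

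**The concern.** Since no listed criterion restricts parity, the trial can enrol women having a first birth together with women who have given birth before. If second-stage durations differ between the two, the pooled standard deviation used by the t test contains that difference as well as the variation between women of like parity. Randomisation balances parity on average, so there is no bias and the error rate is kept. The standard error is nevertheless larger than it need be, and a real shortening is more likely to be missed with the same 77 women per arm.

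A difference in means is collapsible: a linear model with arm and parity targets the same difference in minutes as the t test. Adjustment can therefore recover the lost precision without changing the question. The t test does not touch the binary primary endpoint.

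**Working it through.** **Inputs.** From the protocol: 77 per arm, equal allocation, significance level 0.05 (taken as two-sided, since sidedness is not stated). The document gives no effect size, standard deviation, parity mix or duration. These are assumed below and varied. For the same reason no stated power can be reproduced; only 2 × 77 = 154 can be checked.

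**General relation.** Let R² be the share of outcome variance explained by parity. Approximate power is Φ(d·√(n/2)/√(1−R²) − 1.96). Take the effect that gives 80% power unadjusted: d = (1.960 + 0.842)·√(2/77) = 0.452. Adjusted power is then:

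| R² | 0 | 0.05 | 0.10 | 0.20 | 0.30 | 0.40 |
|---|---|---|---|---|---|---|
| Power | 80.0% | 82.0% | 84.0% | 87.9% | 91.8% | 95.1% |

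**One case by hand.** Lognormal durations, medians 60 min (first birth) and 15 min (later birth), log-SD s = 0.7, half nulliparous (p = 0.5), all durations shortened by 30%.

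- Means: a = 60·exp(0.245) = 76.66 and b = 15·exp(0.245) = 19.16 min.
- Between-parity variance, control arm: p(1−p)(a−b)² = 0.25 × 57.49² = 826.
- Within-parity variance: (exp(s²)−1)(p·a² + (1−p)·b²) = 0.6323 × 3121.9 = 1974.
- R² = 826/(826 + 1974) = 0.30.
- True difference: 0.30 × (76.66 + 19.16)/2 = 14.37 min.
- Unadjusted standard error: √[2800 × (1 + 0.7²)/77] = √54.2 = 7.36 min.
- Adjusted standard error: √{[1974 × 1.49 + 2 × 18.6]/77} = √38.7 = 6.22 min. The 18.6 per arm is what a common parity slope leaves over: slopes 57.49 and 40.25, half the gap 8.62, and 0.25 × 8.62² = 18.6.
- Ratio 6.22/7.36 = 0.845, so the standard error is about 15% smaller.

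Simulation agrees: the average estimated standard error falls from 7.2 to 6.1 min and power rises from 51% to 68%. The simulated relative efficiency is 1.38, so the t test would need about 77 × 1.38 = 106 per arm to match. Simulated t-test power is 65%, 66% and 69% at 105, 110 and 115 per arm.

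**Range of assumptions** (simulation, 10,000 to 20,000 trials per row, 77 per arm, 30% shortening in all women unless stated):

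| Durations (medians, first/later birth) | % nulliparous | t test | Adjusted |
|---|---|---|---|
| Lognormal 60/15, log-SD 0.7 | 30 | 44% | 64% |
| same | 50 | 51% | 68% |
| same | 80 | 67% | 75% |
| same | 95 | 76% | 78% |
| Lognormal 60/15, log-SD 0.5 | 50 | 71% | 94% |
| Lognormal 60/15, log-SD 0.9 | 50 | 36% | 43% |
| Lognormal 60/15, log-SD 0.7, 20% shortening | 50 | 23% | 33% |
| Lognormal 60/15, log-SD 0.7, effect in nulliparous only | 50 | 35% | 46% |
| Lognormal 50/25, log-SD 0.7 | 50 | 69% | 75% |
| Gamma 60/15, CV as log-SD 0.7 | 50 | 50% | 65% |
| Gamma 50/25, CV as log-SD 0.8 | 80 | 58% | 60% |
| Gamma 50/25, CV as log-SD 0.8 | 95 | 62% | 62% |
| No influence of parity | – | 79.2% | 78.8% |

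If only 65 per arm have a second stage, the 60/15, 50% nulliparous cases become 45% to 60% (lognormal) and 43% to 57% (gamma).

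**Validity.** With no effect, rejection rates were 4.7–5.0% for the t test, 4.6–5.0% for the adjusted model and 4.4–4.8% with HC3 robust standard errors. A separate set of 8,000-run simulations (means 60 and 20 min, CV 0.6–0.8, 50–70% nulliparous) gave 4.8–5.6% for the t test and 4.6–5.0% adjusted. There the average estimate was the same under both methods (−15.06 and −15.00 for a true −15), and power rose from 79.4% to 92.1% (R² = 0.36), 64.7% to 74.9% (0.24) and 56.3% to 64.1% (0.17).

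**The case against.** The best counter-argument is that covariates for a secondary endpoint belong in an SAP, and that a short synopsis paragraph naming a default test does not rule out adjusted analyses. An unseen SAP may indeed add a model. But the synopsis is not silent here: it assigns the t test to all continuous data, so this is a stated choice.

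It can also be said that nothing is wrong with a valid test, and that almost any trial could be told a prognostic covariate would help. That stands as a limit on weight: this is an improvement, not the correction of an error.

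Third, that durations differ by parity is not in the document, and the synopsis shows inclusion criteria only. The supportable statement is that no listed criterion restricts parity. If nearly all enrolled women are nulliparous, the gain is 0 to 2 points. This also stands. The case for adjusting survives it, because the loss when parity does not matter is at most 0.4 points, while the possible gain is much larger.

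Two smaller points are fair. The only effect measure the synopsis names is the relative risk, so a mean difference with a confidence interval is an addition to the reporting, though it is what a t test compares. And parity adjustment does not settle how to treat women who never reach the second stage, or those in whom operative delivery ends it.

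**Conclusion.** The concern holds as a minor point of efficiency on one secondary endpoint. The planned t test is valid and unbiased. A parity-adjusted linear model estimates the same difference in mean minutes and, under equal allocation, is more precise whenever parity predicts duration.

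The size cannot be taken from the protocol. Under the assumed inputs the change in power runs from a loss of 0.4 points to a gain of 23 points. With medians of 60/15 min and log-SD 0.7 the gain is 8 to 20 points when 30–80% of women are nulliparous; it nearly disappears at 95%. The equivalent of about 110 women per arm applies only to the 60/15, half-nulliparous lognormal case and should not be read as a general figure. The argument concerns a mean difference and does not carry over automatically to odds ratios for the binary endpoints.

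**What to change.** Add one sentence to the Statistical analysis row, before any outcome data are seen, so that the covariate cannot look selected:

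*Second-stage duration in minutes will be analysed with a linear model including randomised arm and parity (first versus later birth), and the parity-adjusted difference in means will be reported with its 95% confidence interval.*

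Model-based or HC3 robust standard errors both hold the error rate. HC3 power is within about 1.5 points of model-based.

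A parity-adjusted model of log duration, or a parity-stratified rank test (van Elteren), should be supportive at most. In the 60/15, half-nulliparous lognormal case they reach 88% and 86% against 51% for the t test. In the gamma 50/25, 80% nulliparous case they give 46% and 54% against 58%. If only the part of the duration beyond 45 min is shortened (by 60%), they give 13–18% against 37–38%, while the parity-adjusted model in minutes gives 53–54%. The log model also changes the estimand to a ratio of geometric means.

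The cost is that sentence. Parity can be taken from the patient history and second-stage times from the partograms, both already named as sources. No further women or visits are needed.

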# SOC CLINICA OSTETRICIA- GINECOLOGIA

## S. Maria della Misericordia

[name]  
tel. Segreteria Ambulatoriale [name]  
e-mail: [contact]  
Direttore: Prof.ssa [name]

	held by the investigator and/or co-authors; at this meeting, a brief lecture on aspects of primary pelvic floor prevention will be offered to patients in group A, who will also be educated on the perineal massage proposed by the Authors. Group B patients will equally be offered a short lecture on aspects of primary prevention, leaving the patient free choice in pelvic floor education in pregnancy. Group A patients will perform the learned perineal massage at home, reporting their adherence to the study in a diary. After delivery, at the time of discharge, a data collection form regarding postpartum perineal pain will be given to the patient and the date of the 45-day follow-up visit will be communicated.

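### The protocol has no step to keep those who attend the birth and grade the perineum unaware of allocation, although intact perineum is a judgement-dependent endpoint

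*Protocol*

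**What the plan says.** All references are to the protocol synopsis.

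- **Type.** The design is described only as a "Prospective randomized superiority trial". No entry says that anyone is masked, or that the trial is open-label. One centre takes part.
- **Endpoint.** The primary comparison concerns "the absence of vagino-perineal tears (intact perineum"). Secondary comparisons include second-stage duration and bear "on incidence of operative delivery and episiotomies, and on perineal pain and dyspareunia in postpartum".
- **Study design.** Randomisation takes place at the third-trimester visit. The training meeting that follows is "held by the investigator and/or co-authors". Both groups get a short lecture. The difference lies in Group A, "who will also be educated on the perineal massage proposed by the Authors", whose members then massage at home and keep a diary. No sham procedure or diary is described for Group B.
- **Population and data sources.** "Data are collected from the patient history and clinical interview, medical records and partograms, data collection form and written questionnaires". The same entry replaces each woman's name with a number in the database. That is a privacy measure and masks nobody.

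**The concern.** The primary endpoint is binary, and its cut lies between no tear and a minor tear. That is where the examiner's judgement counts most. Episiotomy and operative delivery are decisions taken by whoever conducts the birth. If that person knows the group, a borderline finding may be recorded differently in the two arms. Randomisation balances the arms at entry but does not protect what is observed and written down at birth.

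The setting makes knowledge of allocation plausible. There is one clinic, the massage is the authors' own, the authors or investigator do the training, and only Group A is described as keeping a diary. The women cannot be masked to a massage they perform themselves, so the only place left for protection is the person who grades the perineum, and the protocol provides none there.

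This is a matter of trial conduct that has to be settled before births occur. It is not something a protocol would normally leave to a statistical analysis plan, and no analysis can restore it afterwards.

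**Working it through.** **Reading the document.** Four safeguards were looked for: withholding allocation from labour staff, asking women not to disclose it, separating trainers from graders, and naming an assessor unaware of the group. None is stated.

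**The plan's own figure.** The sample size is 154, with 77 per arm, and 2 × 77 = 154. The synopsis gives no event rates, effect size or power, so the figure cannot be reproduced beyond that sum. The concern does not depend on it.

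**Illustration of size.**

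Inputs from the protocol: n = 77 per arm ('Sample size'); Fisher's exact test and a 0.05 threshold ('Statistical analysis').

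Assumptions, none of them in the protocol:
- the test is two-sided (sidedness is not stated);
- massage has no true effect;
- the true intact rate p is 20%, 30% or 40% in both arms;
- a fraction m of Group A tears is recorded as intact, and no Group B tears are.

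The recorded Group A rate is q = p + m(1 − p). For p = 0.30 and m = 0.10, q = 0.30 + 0.10 × 0.70 = 0.37, a spurious difference of 7 points.

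The chance of a false result favouring massage is the sum of Bin(a; 77, q) × Bin(b; 77, p) over all pairs of counts (a, b) with a > b and a two-sided Fisher p-value below 0.05. Exact enumeration gives:

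| True intact rate p | m = 0 | m = 5% | m = 10% | m = 20% |
|---|---|---|---|---|
| 20% | 1.6% | 6.1% | 16.5% | 54% |
| 30% | 1.7% | 4.9% | 11.5% | 38% |
| 40% | 1.8% | 4.2% | 8.6% | 26% |

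The spurious difference at m = 10% is 8, 7 and 6 points for p = 20%, 30% and 40%.

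**Context.** By the normal approximation (two-sided 0.05), 77 per arm has 80% power for true differences of 20.6, 22.1 and 22.4 points at those control rates. The spurious difference at m = 10% is therefore 8/20.6 = 39%, 7/22.1 = 32% and 6/22.4 = 27% of the detectable difference.

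**The case against.** The strongest reply is that the concern rests on silence in a text headed as a synopsis, and that its factual premises are partly inferred. The protocol does not say who attends births or who grades the perineum. It lists several data sources without assigning the primary endpoint to one. It does not say that the diary or the allocation enters the labour record. A reader might infer from the training arrangement that the trainers also deliver the women and grade their own pupils. The document does not say so, and the point does not need it. What stands is that nothing prevents it, and that birth outcomes can hardly come from anywhere but what birth staff record. A fuller text could exist, but none is shown.

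A second tempting reading is that an attendant's higher threshold for episiotomy in Group A would also push the primary endpoint towards massage. That is not supported. The protocol does not say how an episiotomy counts towards intact perineum. If it makes the perineum non-intact, fewer episiotomies would favour massage. If only tears count, fewer episiotomies could expose more women to spontaneous tears and work the other way. The direction is undetermined, so the argument for the primary endpoint rests on recording alone.

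Third, every rate in the illustration is assumed, and so is the restriction of misrecording to Group A. Equal misrecording in both arms would create no false difference when there is no true effect. This is correct. The table shows how sensitive the test is and does not estimate what will happen in this trial.

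Finally, masking is not free. In one clinic, with eight collaborators listed besides the principal investigator, a woman may mention her group and a trainer may be on duty. That limits how complete the protection can be, but it is no reason to have none.

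**Conclusion.** The concern holds in a limited form. As shown, the protocol has no step to keep those who grade the perineum or decide on episiotomy and operative delivery unaware of allocation. The primary endpoint is sensitive to judgement, and the developers of the massage do the training in the only centre.

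Under the stated assumptions, misrecording 10% of Group A tears would raise the chance of a false significant result favouring massage from about 1.6–1.8% to about 9–17%, the higher figure belonging to the lower control intact rate. These figures rest on assumed intact rates of 20–40%, one-sided misrecording, no true effect and a two-sided test.

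The documents do not support concluding that bias will occur, that allocation leaks by design, or that trainers attend the births. This is an improvement that should be made, not a flaw that invalidates the trial.

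**What to change.** Add a short paragraph to 'Study design':

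1. Allocation and the massage diary are not entered in the obstetric chart or partogram, and women are asked not to tell labour staff their group.
2. The person who grades the perineum at birth is not one of the trainers, where the normal rota allows.
3. Optionally, staff note on the delivery record whether the attendant knew the group, and this is reported descriptively by arm. The data collection form described in 'Study design' is a pain form handed to the woman at discharge, so it is not the place for this item.

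An analysis restricted to births with an unaware attendant should not serve as the check on bias. Awareness arises after randomisation and may differ by arm, so that subset is no longer a randomised comparison. If reported at all, it should be labelled supportive only.

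The cost is one paragraph and, if item 3 is adopted, one item on the delivery record. No extra assessor is needed and the sample size does not change. The downside is that masking will sometimes fail and the rota condition cannot always be met.
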